Part A is a single arm. All subjects will receive 10 µg subcutaneous exenatide twice daily for 5±1 days. The total duration of a subject's participation will be approximately 5 weeks.

Part A – Type and Number of Subjects

- A sufficient number of subjects with T2DM will be screened and enrolled to achieve approximately 10 evaluable subjects.
- If subjects prematurely discontinue the Part A, additional replacement subjects may be enrolled at the discretion of the Investigator in consultation with the Sponsor.

Part A Data Review

Once Part A is complete, data will be reviewed and a decision to progress or not to Part B will be made. A decision to progress to Part B will be made based on the confirmation that change in GMA caused by the administration of exenatide is detectable by an EGG with WLT. Confirmation of safety when adding the WTL on top of a GLP1 receptor agonist will be required to progress to Part B. Adjustments to the study design of Part B (e.g., endpoint evaluation and/or number of subjects) may be made prior to progression to Part B. Details will be described in the Reporting and Analysis Plan (RAP).

Part B: Overall Design

- Part B is randomized, open-label, multicenter, active-controlled, parallel-group study of 8 weeks treatment duration to compare the effects of albiglutide on GMA, GE and nausea as measured by VAS with exenatide as a positive control. The central readers of EGG and GEBT tests will be blinded to assigned treatments.
- Part B will comprise 3 study periods: screening/wash-out (up to 3 weeks), treatment (8 weeks), and post-treatment follow-up (4 weeks).
- Part B will recruit subjects with T2DM (>6 months since diagnosis) with HbA_{1c} >6.5% and ≤9.0%, FPG ≤210 mg/dL (central lab) at screening and on a current regimen of diet and exercise or a stable dose of one OAM (maintained for ≥ 2 months prior to screening).

- Fasting capillary blood glucose will be confirmed to be ≤ 230 mg/dL at baseline.
- Subjects participating in Part A are not allowed to participate in Part B.
- Subjects receiving monotherapy with an OAM of metformin, sulfonylurea, SGLT2-inhibitor, or meglitinide will be washed out for 2 days for immediate release and 4 days for extended release OAM prior to randomization.
- A subject's nutritional plan will be optimized prior to randomization and maintained during the entire study.
- All evaluations and assessments will be performed as outpatient visits.
- Subjects will undergo 4 EGG and 3 GEBT assessments.

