In a head to head, 32-week, open-label clinical trial in patients with T2DM, in which non-inferiority of albiglutide of a 95% confidence interval (CI) upper margin of 0.3% for HbA_{1c} was not met, the incidence of nausea was 9.9% for albiglutide and 29.2% for liraglutide, and the incidence of vomiting 5.0% and 29.3% respectively [Pratley, 2014]. In a 26-week open-label, forced titration clinical trial, nausea was reported in approximately 25.5% and 28% of subjects treated with liraglutide and exenatide, respectively [Buse, 2009]. In exenatide Phase 3 program, nausea was reported in up to 44% of subjects receiving exenatide [Byetta, US Prescribing Information, 2015]. Dulaglutide, another once weekly GLP-1R agonist reported ~20% incidence of nausea at the highest approved dose in the results from pooled placebo-controlled trials [Trulicity, US Prescribing Information, 2015].

The reasons for the differences in incidence of nausea in clinical trials between albiglutide and other GLP-1R agonists are not fully understood. Potential explanations include differences in the pharmacokinetic profiles (e.g., albiglutide T_{max} ~3 days, dulaglutide T_{max} ~2 days, exenatide T_{max} ~2.1 h, or liraglutide T_{max} ~13h). It is unknown if these differences result in compound specific patterns of receptor occupancy and pharmacodynamic response. Differences in molecular size and structure among GLP-1R agonists may also impact penetration through the blood brain barrier and activity in brain receptors.

Electrogastrogram (EGG) is a noninvasive technique to assess GMA [Koch, 2001]. It is used in clinical practice to identify if patients with nausea and other upper GI symptoms without mechanical causes have disturbances in the myoelectrical gastric rhythm, and to confirm the diagnosis of gastroparesis. “EGG with water load test” is a standardized test to induce gastric distention and measure myoelectrical responses as well as collect VAS of upper gastrointestinal symptoms (stomach fullness, hunger, nausea, bloating and abdominal pain) under standardized conditions. The gastric distention produced by the water load induces nausea in a high proportion of patients, allowing the assessment of GMA during the episodes of nausea. Episodes of nausea are typically associated with disturbance in GMA called gastric dysrhythmias.

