To gain insight into a potential peripheral mechanism of nausea associated with GLP-1R agonists; this study will compare the effect of albiglutide and exenatide on GMA, GE and VAS of nausea in T2DM subjects. Albiglutide will be administered weekly at the initial dose of 30 mg and uptitrated to 50 mg after 4 weeks. Exenatide will be administered twice daily at dose of 5 μ g and uptitrated to 10 μ g twice daily after 4 weeks. The study is divided in two parts. Part A will characterize the GMA, GE response and nausea to exenatide and confirm exenatide as a positive control for Part B. Part B will compare the effects of albiglutide and exenatide on GMA, GE and nausea.

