4.4. Design Justification

- This study is designed to gain insight into a potential peripheral mechanism of nausea associated with GLP-1R agonists and to determine if this mechanism can explain the clinically observed difference in GI tolerability between albiglutide and exenatide in clinical trials. This study will compare the effect of albiglutide and exenatide on GMA, GE and VAS of nausea in T2DM subjects.
- The study population, indication and doses of albiglutide and exenatide used in this study are consistent with the approved prescribing information (PI) for albiglutide and exenatide, respectively.
- The treatment duration will allow the evaluation of GMA, GE and VAS of nausea at expected steady-state and over time for both medications.
- EGG, GE and VAS of nausea will be assessed at the timing of expected C_{max} .
- Exenatide, a short acting GLP-1R agonist is used as a positive control. In the exenatide Phase 3 program, nausea was reported in up to 44% of subjects receiving exenatide [Byetta, US Prescribing Information, 2015]. Clinical data comparing albiglutide with exenatide is available from the albiglutide Phase 2b study [Rosenstock, 2009].
- The response of GMA to GLP-1R agonists has not been characterized in humans. Therefore, the study will be conducted in two phases (Part A and Part B). Part A will characterize the effects of exenatide on GMA, GE, and nausea and confirm exenatide as a positive control for Part B. Part B will compare the effects of albiglutide to exenatide on GMA, GE and nausea.

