7.3.1. EGG

Subjects should have nothing to eat or drink from midnight prior to the EGG. Two hours before the EGG subjects will be provided one piece of toast and 4 US fluid ounces (120 mL) of apple juice. This provides a small amount of calories so subjects are not “starving” and also provides a consistent EGG baseline before the water load. Subjects should not have anything further to eat or drink until after the EGG procedure.

EGG is recorded with ECG-type electrodes placed on the surface of the epigastrium. The EGG signals are recorded on a strip chart for visual analysis and digitized simultaneously for computer analysis. The EGG recordings include a 15-min baseline tracing after which the subjects ingest water for 5-min until they perceive their stomach is full. All subjects will rate symptoms experienced immediately before and 10, 20 and 30 min after ingestion of the water.

A VAS (0-100 mm) will be used to assess the intensity of the following sensations: no nausea (0) to severe nausea (100), stomach empty (0) to stomach full (100), hunger (0) to

satiety (100) and no bloating (0) to severe bloating (100). The recording channel with the clearest electrogastrographic signal will be chosen for visual and computer analysis.

The details of test procedures for EGG with water load test are provided in the SRM.

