7.4.1. Adverse Events (AE) and Serious Adverse Events (SAEs)

The definitions of an AE or SAE can be found in [Appendix 6](#).

The investigator and their designees are responsible for detecting, documenting and reporting events that meet the definition of an AE or SAE.

Events of nausea, hunger, stomach fullness, bloating, and abdominal pain resulting from the water load test will be captured and reported as an endpoint through the VAS and will not be considered an AE. Any of these 5 events reported outside of the timings of the VAS collection should be recorded as an AE/SAE if meets the definition as noted in [Appendix 6](#).

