9.2. Part B: Statistical Considerations and Data Analysis

9.2.1. Hypotheses

Hypotheses testing in Part B will be performed for the parameters listed in Section 3.2 to compare albiglutide to exenatide in subjects with T2DM for a treatment period of 8 weeks.

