9.2.4. Key Elements of Analysis Plan

9.2.4.1. Primary Analysis

The primary endpoint is change from baseline in EGG parameters at Week 2, 5, and 8 at each time interval (pre-and 10, 20 and 30 min after water load). The primary endpoint is change in GMA as assessed by EGG parameters: change from baseline of distribution of average power by frequency region (as % of power); change from baseline of ratios of average power post-water load test (post-WLT)/pre water load test (pre-WLT) by frequency region; and change from baseline of percentage (%) of time with the dominant EGG frequencies in the four frequency ranges (bradygastria, normal, tachygastria and duodenal). The primary analyses of the primary EGG parameters will be conducted using mixed-effect model with repeated measures (MMRM). The MMRM model will include the EGG parameter as the dependent variable; treatment group, time interval, visit week, and treatment-by-week interaction as fixed effects; the relevant parameter baseline as covariate; and subject as a random effect.

The primary endpoint of change from baseline in EGG parameters related to VAS of nausea at Week 2, 5, and 8 at each time interval (pre-and 10, 20 and 30 min after water load) will be analyzed using the MMRM method as described above. The MMRM model will include the EGG parameter as the dependent variable (the same EGG parameters as listed above); treatment group, time interval, visit week, and treatment-by-week interaction as fixed effects; the relevant parameter baseline as covariate; VAS of nausea as time varying covariate; and subject as a random effect.

Treatment effects estimates (and associated 95% CI) of albiglutide will be evaluated within this MMRM model as least squares means contrasts relative to exenatide. An unstructured covariance matrix will be used for the MMRM analysis, unless the model does not converge, in which case the covariance matrix will be decided upon model convergence status and the Akaike information criterion.

Part B analysis is further described in the RAP.

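### Part B is declared to compare the two drugs on nausea VAS, but Sections 3.2 and 9.2.4 never make nausea VAS an outcome, so the plan gives no between-drug nausea estimate under the water load test

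*Protocol*

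**What the plan says.** Several places state that nausea VAS will be compared. The synopsis and Section 4.3.1 describe Part B as a study "to compare the effects of albiglutide on GMA, GE and nausea as measured by VAS with exenatide as a positive control". Section 2.1 says "this study will compare the effect of albiglutide and exenatide on GMA, GE and VAS of nausea in T2DM subjects", and Section 4.4 repeats this. Section 4.4 also gives the purpose: "to determine if this mechanism can explain the clinically observed difference in GI tolerability between albiglutide and exenatide".

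The data are to be collected. Section 2.1 names five VAS symptoms, nausea among them. Section 7.3.1 defines a 0-100 mm nausea scale, rated just before and 10, 20 and 30 minutes after the water load. Section 7.4.1 says that nausea caused by the water load "will be captured and reported as an endpoint through the VAS" and is not an adverse event.

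On testing, Section 9.2.1 says: "Hypotheses testing in Part B will be performed for the parameters listed in Section 3.2 to compare albiglutide to exenatide". Section 3.2 lists a VAS endpoint for fullness, hunger, bloating and abdominal pain. Its only line that mentions nausea VAS has the EGG parameters as the endpoint. Section 9.2.4.1 describes two MMRMs, both with an EGG parameter as dependent variable; the second adds "VAS of nausea as time varying covariate". Section 9.2.4.2 gives an MMRM to the same four VAS symptoms. It leaves the Gastroparesis Cardinal Symptom Index diary (GCSI-DD) and nausea adverse events outside the water load test to descriptive statistics.

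**The concern.** The mechanism question has three links: drug to gastric myoelectrical activity (GMA), GMA to nausea, and drug to nausea. The first primary model addresses the first link and the second primary model the second. The third, measured in the same test session as the EGG, has no endpoint and no model.

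Without it, a GMA difference between the drugs could not be set beside an estimate, with confidence interval, of the nausea difference in the same sessions. The other planned nausea data are descriptive, and Section 7.4.1 removes water-load nausea from the adverse events, which leaves the VAS as its main record.

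A smaller matter is the sentence on treatment contrasts in Section 9.2.4.1. It refers to one MMRM in the singular after two have been described. On-treatment nausea is a post-randomisation variable, so a contrast adjusted for it is in general not the total effect on GMA.

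**Working it through.** **The plan's own number.** The target is 50 evaluable subjects with 20% withdrawal: 50 / 0.8 = 62.5, against 62 stated; 62 × 0.8 = 49.6, about 50. The figure reproduces, and nothing below changes it. Section 9.2.2.1 rests the size on feasibility, so there is no power calculation to check.

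**Passages side by side (Protocol).**

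| Place | Fullness, hunger, bloating, abdominal pain | Nausea |
|---|---|---|
| Aim and design statements: 1, 2.1, 4.3.1, 4.4 | Not named as a compared effect | Named as a compared effect |
| 7.4.1 | VAS endpoint, not an adverse event | VAS endpoint, not an adverse event |
| 3.2 | Secondary endpoint, Weeks 2, 5 and 8 | Only as something the EGG parameters are related to |
| 9.2.4.1 | Absent | Covariate in the second EGG model |
| 9.2.4.2 | Outcome, MMRM | VAS absent; GCSI-DD and adverse events descriptive |
| 9.2.4.3 | Absent | Absent |

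Part B endpoints or models with nausea VAS as outcome: 0. Models with it as covariate: 1. VAS symptoms with a planned between-drug comparison: 4 of 5.

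**What the added model would estimate.** The MMRM in Section 9.2.4.1 has treatment, interval, week and treatment-by-week, with no treatment-by-interval term. Reused for nausea, it gives one contrast per week, common to the four intervals.

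*Approximate precision.* Assume 25 per arm, an equal SD at each interval, a common correlation ρ between intervals and no baseline adjustment. In units of the within-arm SD of the change at one interval:

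- one interval alone: t(0.975, 48) × √(2/25) = 2.011 × 0.283 = 0.569 SD;
- mean of four intervals: 0.569 × √((1 + 3ρ)/4), which is 0.39, 0.45 and 0.50 SD for ρ = 0.3, 0.5 and 0.7.

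The second line is the closer guide to the weekly contrast. The values of ρ are assumptions.

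**The two EGG contrasts.** For a single assessment with within-arm SDs set to 1, adjusted contrast = d − s·g. Here d is the total effect on the EGG parameter, g the nausea difference (albiglutide minus exenatide) and s the within-arm slope of the EGG parameter on nausea. The documents give neither g nor s. Section 2.1 reports nausea or vomiting below 10% each week on albiglutide 30 mg and a peak of 29% on exenatide, which points to g below zero. Then −s·g is positive if the EGG parameter rises with nausea and negative if it falls. With assumed g = −0.5, s = 0.4 shifts the contrast by −(0.4)(−0.5) = +0.20 SD and s = −0.4 shifts it by −0.20 SD. With g = 0 or s = 0 the shift is nil. This shows direction only; it is not an estimate for the planned repeated-measures model.

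**The case against.** **The GMA-nausea link is already in the plan.** A reader might infer from the missing endpoint that this link would rest only on descriptive diary and adverse event data. The documents do not support that: the second primary model regresses each EGG parameter on concurrent nausea VAS and so estimates the association, at primary level. This stands, and it narrows the point to the between-drug nausea contrast, which a model with an EGG parameter as dependent variable cannot supply.

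**The plan was open to refinement.** Sections 4.2 and 9.1.4.2 let endpoints and their assessment be refined in the Reporting and Analysis Plan (RAP) after Part A without a protocol amendment. Section 9.2.1 does not say that only the Section 3.2 parameters may be tested. Both are true, and the lack of a Part B RAP follows from early termination, not from a drafting lapse. But permission to refine does not supply the comparison; the RAP provided covers Part A only. Section 9.2.4.2 introduces its list in open terms but refers to Section 3.2 for the definitions, and nausea VAS is not an outcome there.

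**The contrast sentence is general.** A reader might infer that the primary effect on GMA would be the nausea-adjusted contrast. The text does not support that either. The first paragraph of Section 9.2.4.1 ties change in GMA to the model without nausea, and the contrast sentence is followed by a covariance rule for the MMRM analysis as a whole. If it covered the second model alone, the first would have no treatment contrast. The natural reading is that it covers both, so only a clarification is warranted.

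**Conclusion.** The point holds as an omission. Part B is declared to compare the drugs on nausea VAS, the scale is defined and its collection scheduled, and water-load nausea is called an endpoint. Sections 3.2 and 9.2.4, followed as written, nevertheless give no between-drug estimate for it. Its size is one of five VAS symptoms, and it is the symptom the study sets out to explain. This conclusion rests on the text alone.

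The precision range of 0.39 to 0.50 SD depends on the assumed correlations and a simplified model. The gap between the EGG contrasts with and without nausea adjustment is unknown from the documents. It could be nil, and its sign depends on the direction of both the nausea difference and the EGG-nausea slope.

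Part B is exploratory, sized on feasibility, and did not run. No reported result is affected; the point matters for the written plan and for any reuse of the design.

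**What to change.** 1. Add a secondary endpoint to Sections 3.2 and 9.2.4.2: change from baseline in nausea VAS at Weeks 2, 5 and 8, before the water load and 10, 20 and 30 minutes after it. Mirror it in the synopsis. Analyse it with the same MMRM as the other four VAS items, and state that the model as specified gives treatment contrasts by week, common across intervals.
2. As a minor clarification in Section 9.2.4.1, state that the treatment effect on GMA is the contrast from the model without nausea VAS. Label any treatment contrast from the model with nausea VAS as conditional on a post-randomisation variable. The second model keeps its place as the analysis of EGG parameters in relation to nausea.

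The cost is one endpoint line, one extra exploratory MMRM on data already scheduled at every EGG, and a clarifying sentence or two. Sample size, visits and burden on subjects do not change.

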9.2.4.2. Secondary analyses

The relative effects of albiglutide compared to exenatide will also be assessed across a number of secondary endpoints. The secondary endpoints are defined in Section 3.2 and include change from baseline in $T_{1/2}$ at Week 5 and 8; change from baseline in kPCD of GE at Week 5 and 8 and at each time interval (45, 90, 120, 150, 180 and 240 min); change from baseline volume of water ingested during water load EGG test Week 2, 5 and 8; and change from baseline of VAS of stomach fullness, hunger, bloating and abdominal pain during the EGG water load test at Week 2, 5, and 8. The secondary endpoints will be analyzed analogous to the primary endpoint using MMRM. In addition, summary statistics (including number of subjects, mean, median, min, max, SD, SE) and graphical displays will be provided.

The overall general safety and tolerability of albiglutide versus exenatide will be evaluated in tabular and/or graphical format and summarized descriptively.

Vital signs, clinical laboratory tests, adverse events (AEs), Gastroparesis Cardinal Symptom Index – Daily Diary (GCSI-DD), and nausea AEs presenting outside the timing of the WLT and GCSI-DD will be assessed using descriptive statistics.

9.2.4.3. Exploratory analyses

The exploratory endpoint number and % of subjects with a shift in gastric rhythm status will be summarized descriptively by treatment group. In addition, the number and percentage of subjects by gastric rhythm status will be provided by time interval and visit. The mean and mean change from baseline in average dominate frequency will be summarized using descriptive statistics.

The details of any further planned analyses, including subgroup analysis, will be provided in the RAP. Moreover, the relationship between EGG parameters and FPG and HbA1c will be examined.

10. STUDY GOVERNANCE CONSIDERATIONS

10.1. Posting of Information on Publicly Available Clinical Trial Registers

Study information from this protocol will be posted on publicly available clinical trial registers before enrollment of subjects begins.

10.2. Regulatory and Ethical Considerations, Including the Informed Consent Process

Prior to initiation of a site, GSK/designee will obtain favourable opinion/approval from the appropriate regulatory agency to conduct the study in accordance with ICH Good Clinical Practice (GCP) and applicable country-specific regulatory requirements.

The study will be conducted in accordance with all applicable regulatory requirements, and with GSK policy.

The study will also be conducted in accordance with ICH Good Clinical Practice (GCP), all applicable subject privacy requirements, and the guiding principles of the current version of the Declaration of Helsinki 2008 (which is based on the initial version enacted in 1996). This includes, but is not limited to, the following:

- IRB/IEC review and favorable opinion/approval of the study protocol and amendments as applicable
- Obtaining signed informed consent for each subject prior to participation in the study.
- Investigator reporting requirements (e.g. reporting of AEs/SAEs/protocol deviations to IRB/IEC)
- GSK/designee will provide full details of the above procedures, either verbally, in writing, or both.

The IEC/IRB, and where applicable the regulatory authority, approve the clinical protocol and all optional assessments, including genetic research.

- Optional assessments (including those in a separate protocol and/or under separate informed consent) and the clinical protocol should be concurrently submitted for approval unless regulation requires separate submission.
- Approval of the optional assessments may occur after approval is granted for the clinical protocol where required by regulatory authorities. In this situation, written approval of the clinical protocol should state that approval of optional assessments is being deferred and the study, with the exception of the optional assessments, can be initiated.

